#### **7.3.4 Handling of Missing Data**

To address missing data, we will review the frequency of missing and non-missing values for all variables at baseline and follow-up. We will conduct missing value analyses to determine whether persons with missing values are systematically different from those without missing values. If this assessment of the frequency of missing data suggests that bias may be introduced, we will employ multiple imputation to address the missing data.

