### Implementation Feasibility Measures

Measures indicating feasibility of implementation include recruitment rate (% screened who are deemed eligible, % screened who proceed to consent and enrollment), retention rate (% enrolled who complete post-survey), time from recruitment initiation to sample saturation, and intervention engagement (message response rate and mean response time).

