## **7.3 Statistical Method**

### **7.3.1 Statistical Design**

The pilot trial features a single-group, pre-post quasi-experimental design. As this is a feasibility study, hypothesis testing on the main effectiveness outcomes is strictly exploratory. Analysis assumes a null hypothesis of no participant-level change in the outcome measures from baseline to follow-up. Inferential analysis will be conducted on all outcome measures described in 7.1.3.

Basic descriptive statistics will be calculated for feasibility, acceptability, and outcome measures. We will present frequency tables for the categorical variables and means, standard deviations, and percentiles (25th, 50th, 75th) for the continuous variables. For outcome

measures, descriptive statistics will be calculated for baseline scores, follow-up scores, and change in scores.

Inferential analysis will be conducted on participant-level change in outcome measures from pre to post using paired t-tests (or Wilcoxon signed-ran tests if response distributions are non-normal). We will also examine differences in mean change scores across levels of each demographic variable using ANOVA. Significance levels for analyses will be set at  $\alpha=0.05$ . We will use R version 4.3.0 for data cleaning, management, and analysis.

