### **7.3.2 Sample Size Considerations**

The proposed sample size is 30. As the primary goal is to assess feasibility and acceptability, not effectiveness, sample size is not based on anticipated effect sizes. Previous guidance has indicated our proposed sample size is an acceptable number for feasibility studies. This sample size will allow us to estimate the retention rate to within a 95% confidence interval of +/- 12% (calculated assuming a retention rate of 85%). Although exploratory only, the sample size will further allow us to detect moderate effect sizes in the continuous outcomes (Cohen's  $d = 0.53$ ) with 80% power (alpha = .05, two-tailed) using paired t-tests. Power calculations were performed using G\*Power 3.1.9.7.

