### **7.3.3 Planned Analyses**

#### **7.3.3.1 Primary Analyses**

The primary outcomes (stigma resistance and self-stigma) and secondary outcomes (hope and self-esteem) will each be measured at baseline and follow-up for all participants. The effectiveness of the intervention will be measured as the mean change in participant-level outcome scores from pre to post given the null hypothesis of no change and a type I error rate of 0.05. We will use an intention-to-treat approach, including all participants with complete pre and post data in analysis regardless of adherence.

Feasibility and acceptability will be characterized descriptively, as described in 7.4.1.

Follow-up telephone interviews will be transcribed and computerized for analysis in the qualitative data analysis program Dedoose (v9.0). Transcripts will be coded and analyzed for emerging themes on intervention acceptability using the Braun & Clarke (2006) approach to reflexive thematic analysis (TA).

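### Missing outcomes are addressed only if an undefined comparison of about 4–5 non-returners with 25–26 returners suggests bias, and that comparison cannot support a conclusion of no attrition bias

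*Combined protocol and SAP*

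**What the plan says.** Section 7.3.3.1 describes its approach as intention-to-treat but sets the analysis population as "including all participants with complete pre and post data in analysis regardless of adherence". Anyone who misses the follow-up survey is therefore outside the paired analysis of stigma resistance and self-stigma.

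Section 7.3.4 is the only provision for those people. It begins with a review of how often values are missing for every variable at both time points. It continues: "We will conduct missing value analyses to determine whether persons with missing values are systematically different from those without missing values". The consequence is conditional: "If this assessment of the frequency of missing data suggests that bias may be introduced, we will employ multiple imputation". The section names no test, no significance level, no variables to compare and no amount of missing data that would start imputation. No other sensitivity analysis is planned.

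The numbers come from 7.3.2. "The proposed sample size is 30", and the precision of the retention estimate is "calculated assuming a retention rate of 85" per cent. Retention is defined under Implementation Feasibility Measures (7.1.3) as "retention rate (% enrolled who complete post-survey" among those enrolled.

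**The concern.** A rule of this kind makes the treatment of missing outcomes depend on the result of a preliminary check. That is defensible only if the check can tell harmless from harmful attrition. With four or five people on one side, a finding of no difference is the likely result under quite large true differences, and could be taken as evidence that the completers are representative.

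The check also looks at the wrong quantity. A pre-post mean is biased when non-returners' change differs from completers' change. Similar baseline values do not rule that out, and different baseline values do not establish it.

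At stake is how the change in the two stigma scales is read. Section 5.1 names these as the primary outcomes, and 5.2.1 says preliminary effectiveness is one of the results that could lead to future trials.

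**Working it through.** **Inputs from the plan.** N = 30 and assumed retention 85% (7.3.2); general significance level 0.05 (7.3.1); complete-case paired analysis (7.3.3.1); four baseline scale scores and five categorical covariates (7.1.3).

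**Inputs assumed, because the plan gives none.** The true baseline difference between returners and non-returners (0.5 to 1.0 SD shown); the difference in their change (0.5 to 1 SD); the test used in 7.3.4 (two-sample t-test or Fisher's exact test, two-sided 0.05); and the correlation between variables (0 to 0.5).

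**1. The plan's own figure.** Section 7.3.2 claims d = 0.53 "with 80% power (alpha = .05, two-tailed) using paired t-tests". The noncentrality is 0.53 × √30 = 2.90 on 29 df, which gives power 80.1%. The stated figure reproduces.

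**2. Group sizes.** Expected non-returners: 30 × 0.15 = 4.5, so 4 vs 26 or 5 vs 25.

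**3. Power of one comparison.** The noncentrality is d × √(n₁n₂/(n₁+n₂)) on 28 df. The multiplier is √(4×26/30) = 1.86 or √(5×25/30) = 2.04.

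| True difference | 4 vs 26 | 5 vs 25 |
|---|---|---|
| 0.5 SD | 14.7% | 16.7% |
| 0.8 SD | 30.1% | 35.1% |
| 1.0 SD | 43.6% | 50.4% |
| Difference for 80% power | 1.56 SD | 1.42 SD |

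Poorer retention helps little: at 8 vs 22, power for 0.5 SD is 22%.

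**4. A binary trait (Fisher's exact test).** If 20% of non-returners and 50% of returners have the trait, power is 7% (4 vs 26) or 12% (5 vs 25). With the rates reversed it is 21% or 24%.

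**5. Several variables, each tested at 0.05 without adjustment.** Simulated chance that at least one is significant, over both splits and correlations from 0.5 to 0:
- no true difference, four scale scores: about 16–20%;
- no true difference, nine variables (all treated as continuous): about 28–38%;
- a true 0.5 SD difference on all four scores: about 36–52%;
- a true 0.8 SD difference on all four scores: about 59–82%.

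So the unstated number of tests largely determines how often the trigger fires, with or without a real difference.

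**6. Size of the bias.** The completers' mean differs from the all-enrolled mean by (proportion missing) × (difference in change between completers and non-returners): 0.15 × 0.5 = 0.075 SD and 0.15 × 1 = 0.15 SD. The standard error of the completers' mean change is 1/√25 = 0.20 SD.

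**7. What a sensitivity analysis must span.** Let k non-returners have mean change s, and 30 − k completers mean change m, in SDs of the change score with improvement positive. The all-enrolled mean is [(30 − k)m + ks]/30.
- No change (s = 0): the factor on m is 25/30 = 0.83 or 26/30 = 0.87.
- Direction is lost at s = −(30 − k)m/k. For m = 0.20: −25×0.20/5 = −1.0 to −26×0.20/4 = −1.3. For m = 0.53: −25×0.53/5 = −2.65 to −26×0.53/4 = −3.45.
- A shift of 0.5 SD moves the overall mean by only 0.5×4/30 = 0.07 to 0.5×5/30 = 0.08, so a grid that stops there would nearly always look robust.

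**The case against.** The strongest reply is that 7.3.4 contains no significance rule. The trigger is worded partly as a judgement about how much is missing, and 15% missing could by itself lead the team to impute. That stands. A reader might infer that the safeguard has almost no chance of finding a difference and so will almost never act. The documents do not support this: no test is specified, one test would find a 1.0 SD difference 44–50% of the time, and several unadjusted tests would fire quite often.

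A reader might also infer that the comparison is confined to baseline data. It is not. Message response rate and response time are collected during the intervention (7.1.3), and off-study reasons are recorded for every participant (7.2.6). Section 7.3.4 covers all variables, so people who return but skip items also count as having missing values, and that group may exceed 4–5. These data make the description richer. They still do not show a non-returner's change in stigma, and the weekly message ratings are anonymous, so they cannot be linked to anyone.

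Finally, effectiveness testing is declared exploratory (7.3.1), 4.1 promises descriptive presentation, retention is itself reported, and the plausible bias is below one standard error of the mean change. This is fair and limits the weight of the point. It does not justify making the analysis conditional on an uninformative check, when running it every time costs almost nothing.

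**Conclusion.** The point holds in a limited form. The trigger in 7.3.4 is undefined. Read as a single test at the plan's 85% retention, it has 15–17% power for a 0.5 SD difference and 30–35% for 0.8 SD; read as several unadjusted tests, it can fire on noise. Under either reading it does not observe the quantity that causes bias. A null result therefore cannot support a conclusion that attrition is harmless, and the comparison should not decide whether missing outcomes are addressed. Writing in a cut-off would make the rule reproducible but would not cure this.

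The consequence is modest: 0.075–0.15 SD in the mean change if non-returners' change differs by 0.5–1 SD, against the plan's detectable 0.53. These figures rest on 85% retention being realised and on assumed differences that the documents do not supply. This is a cheap improvement to an exploratory analysis, and it leaves the feasibility aims untouched.

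**What to change.** In 7.3.4:

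1. Delete the condition on multiple imputation.
2. Keep the comparison of people with and without missing values as description only: standardized differences at baseline, message engagement and off-study reasons, with no test and no decision attached.
3. In every case, report beside the complete-case result one sensitivity analysis on all enrolled participants for stigma resistance and self-stigma. Use the multiple imputation already planned, so that the variance reflects the imputation. Centre non-returners' change at none, then shift it in the unfavourable direction for each scale over a range wide enough to reach the tipping point. State the shift at which the direction of the mean change is lost. On the figures above, the range must extend beyond 1 SD, and to about 3.5 SD if completers improve by 0.53 SD.

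The cost is SAP wording and a few table rows, with no new data or participants. The downside is a less precise and somewhat smaller all-enrolled estimate, about 0.83–0.87 of the completers' mean under no change.

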## 8. Trial Administration

### 8.1 Ethical Considerations: Informed Consent/Accent and HIPAA Authorization

Written voluntary informed consent will be obtained from each study participant. The consent procedures will be conducted with prospective participants before any study activities are carried out.

The informed consent procedure follows the UNC-Chapel Hill required consent template including describing the purpose of the study, the procedures to be followed, and the risks and benefits of participation. The consent forms will use language that is sufficiently simple for lay persons to comprehend.

Participants who are eligible for the study will be approached by a study team member regarding the possibility of participating in the study. They will be reassured that their decision to participate in the study or not will not affect their relationship with any program or organization, including but not limited to UNC-Chapel Hill and the SHRPS harm reduction program. If the participant is agreeable, the study coordinator will explain the study in-depth in plain language, including the possible risks and benefits to participating in the study. After reviewing the informed consent form, the study team member will reiterate that participation is voluntary and then provide time and opportunity for the participant to review the document again and ask any questions or share any concerns. Once all questions have been answered, prospective participants will be told they have the opportunity to provide informed consent, decline to participate, or take additional time to consider participation (e.g. go home and return later). If they agree to participate, the study team member and participant will both sign and date the informed consent form. The participant will be offered a hard copy of the form to take home.

Study staff performing consent procedures will be trained to probe for comprehension to ensure the participant understands the purpose and procedures of the study, their rights as a research participant, the voluntariness of the study, and the risks and benefits of participation.

### 8.2 Institutional Review Board (IRB) Review

This protocol, the informed consent documents, and any subsequent modifications will be reviewed and approved by the UNC-Chapel Hill Institutional Review Board responsible for the oversight of the study. Annual IRB reporting and review is required for the duration of the study.

### 8.3 Subject Privacy, Confidentiality & Data Management

We will take the utmost caution to protect the confidentiality of participants' involvement in the study and all participant provided information/data throughout all research procedures and data management and analysis. Participants may be concerned about the security of their data, particularly since it is collected and stored electronically. Every effort will be made to ensure that study participants are protected from the risk of breach of confidentiality using a variety of steps to ensure participant data security across all sources.

The results of the research will be disseminated but no participant names or other identifying information will be used in any dissemination materials (published or otherwise).

## 8.4 Data Collection

Surveys will be completed by participants via Computer-Assisted Self-Interview (CASI) at the baseline follow-up study visits using Qualtrics. Participants will complete the survey in a private room. A trained study team member will be available to answer questions. Follow-up telephone interviews, conducted with a subsample of participants (n=12), will be completed within two weeks of the participant's follow-up study visit. Study data will be stored in a secure, password-protected database on UNC-Chapel Hill servers. Survey and interview data will be uploaded to the database daily.

Participant-related study information will be identified through a participant ID number (PID), derived from the participant's date of enrollment, on all participant case report forms, audio files, transcripts, and CASI files. Participant names or other personally identifying information will not be used on any study documents and will be redacted from interview transcripts.

## 8.5 Data Quality Assurance

The quality assurance (QA) plan will include the following components:

- Develop standard operating procedures (SOPs) for important processes of the study, including those involving:
  - The data (including: contacting potential participants, data collection, data entry, data cleaning, data storage and transmission);
    - Systematic plan for data cleaning: Data management staff will be responsible for systematically cleaning the data on a regular basis, at least weekly, to prevent systematic problems with data collection from occurring. Discrepancies in data or missing data found during data cleaning will be investigated by the data manager by meeting with the survey administrator and data management team and referring to source documents, when applicable.
  - Modifications of a procedure that may change during the course of the study (due to reasons such as newly published data, guidelines, or changes in local policies or regulations, etc.). Revisions should be documented with the date of change and approved by the PI; all changes must be documented and communicated to the study staff.
- Ensuring all study staff are trained on relevant SOPs (including the protocol they are carrying out and all data collection forms), before study initiation and annually thereafter with refresher trainings.
- Ensuring all interviewers are extensively trained and will practice conducting study-related interviews, for both qualitative and quantitative data collection.
- Data management staff will produce data error reports on a weekly basis. The Data Manager will review data error reports weekly, and immediately bring any errors identified to the attention of appropriate staff for correction. Errors will be corrected within 3 working days of identification.

- Data entry and transmission reports generated by the electronic data system, if applicable, will be reviewed by the data manager to assure that transmitted data was successfully entered into the database. Errors will be brought to the attention of the responsible person and corrected within 3 working days of identification.
- New data staff members will have all records reviewed by the data manager during their first 1-2 months of employment or until their competency is determined to be at the level of other staff. If necessary, a more intense monitoring regimen is instituted according to the auditing results and needs of the new staff member.

Quality assurance checks will be implemented throughout the data collection process to quickly identify and rectify potential problems. Survey instruments will employ skip patterns and built-in checks to minimize discrepant and unrealistic answers. Standard data cleaning procedures will be used prior to analyses, including outlier detection and graphical representation of the data.

## **8.6 Access to Source**

The study PI and mentor will ensure the availability of all study-related records for audit by NIH, NIDA, and UNC IRB, including participant records, consent forms, case report forms, and supporting source documentation for the purpose of ensuring the protection of study participants, compliance with the protocol and regulatory policies, and accuracy and completeness of records.

## **8.7 Data or Specimen Storage/Security**

All records will be identified by coded number only to maintain participant confidentiality. The data collected from individuals will be stored using a numerical system to identify each subject. Only the staff working on this study (Principal Investigator and Co-Investigators) will have access to the records and identities of the subjects. Any physical study-related information (e.g., informed consent forms) will be stored securely in locked filing cabinets with access limited to authorized study staff. All records that contain names or other personal identifiers, such as locator forms and informed consent forms, will be stored separately from study records identified by code number. Electronic study records, e.g., survey responses, interview transcripts, and case report forms, will be stored on a secure, password-protected university-hosted server (Microsoft OneDrive/SharePoint). Only study staff approved by the UNC IRB will have access to the server.

Qualtrics. Qualtrics will be used for study surveys. The UNC Information Security Office has approved Qualtrics for collection and storage of Private Health Information (PHI) and a Business Associates Agreement (BAA) is in place between UNC-Chapel Hill and Qualtrics. Qualtrics uses Transport Layer Security (TLS) encryption (also known as Hypertext Transfer Protocol Secure (HTTPS)) for all transmitted data. Survey data are protected with passwords and HTTPS referrer checking. The data is hosted by third party data centers that are Statement on Standards for Attestation Engagements (SSAE)-16 Service Organization Control (SOC) II certified. All data at rest are encrypted, and data on deprecated hard drives are destroyed by U.S. Department of Defense methods and delivered to a third-party data destruction service. Qualtrics deploys the general requirements set forth by many Federal Acts including the Federal Information Security Management Act (FISMA) of 2002. They meet or exceed the minimum requirements as outlined in Federal Information Processing Standards (FIPS) Publication 200.

Twilio. Twilio is a third-party vendor that will be used for transmitting intervention text messages to participants. Twilio uses end-to-end encryption and follows industry-standard security measures, certified under ISO/IEC 27001 with additional attestations to ISO/IEC 27017 and ISO/IEC 27018. Twilio uses TLS 1.2 to encrypt data in transit between the customer application and Twilio over public networks. Databases housing customer data are encrypted at rest. Twilio is among the most commonly used softwares for transmission of text messages in mHealth intervention trials.

### **8.8 Retention of Records**

We will permanently delete identifying information from the computer server 4 weeks after data collection ends, including participant contact information logs. Only a completely de-identified copy of the dataset will remain on the server after this point. The de-identified copy of the dataset will be deleted five years after study data are published, as required by most journals.

Interview audio files will be uploaded to the secure server within 24 hours of the interview then deleted from the recording device. The audio will be transcribed to text and stored on the server within one week, after which the audio file will be immediately and permanently deleted from the server.

### **8.9 Data Safety Monitoring Plan**

Reporting of AEs and SAEs. Adverse incidents will be reported to the UNC Institutional Review Board and NIH project officers. Potential incidents may include protocol violations, security incidents, breach of confidentiality, or adverse psychological reactions to the intervention.

In case of any adverse event, site study staff will record the incident in the adverse event tracking log and report the incident in writing via email to the PI and mentor within 24 hours of discovering the adverse event. Any adverse events or protocol violations will also be reported to the UNC IRB and NIH within 5-10 days (depending on severity and needed information collection) with follow-up reporting of any pending information, action, or follow-up.

All SAEs will be reported by the PI to the IRB as soon as possible and reported to NIDA within 24 hours of the event by email. A written follow-up must be received by NIDA within 72 hours of the event. The written follow-up will include the date of the event, what occurred, actions taken by project staff, planned follow-up (if any), whether the event appears to be related to the intervention or participation in the study, and whether the participant will continue in the study.

All AE/SAE will also be included in the annual report to NIDA.

Reporting of IRB Actions to NIDA. IRB actions will be reported by the PI to NIDA within 5 working days.

Reporting of Changes or Amendments to the Protocol. Changes or amendments to the protocol will be reported to NIDA within 5 working days.

Process of AE/SAE Collection. Serious adverse events are based on the FDA definition and defined as those that result in death, are life-threatening, result in hospitalization or prolongation of existing hospitalization, a persistent or significant disability, a congenital abnormality or birth defect. Other injuries or medical events may be considered to be serious adverse events when, in the opinion of a physician, they may jeopardize the participant and may require medical or

surgical intervention to prevent one of the above outcomes. For the purposes of this study, substance abuse or dependency alone in the absence of other adverse impact will not be considered to be an adverse event.

**AE/SAE Follow-up Plan.** Reports on AEs and SAEs will be reviewed yearly by the PI, mentor, and co-investigators and included in annual reports to the IRB and NIDA. *See Section 4.2 above for details on AE/SAE reporting.*

Additionally, study staff will remind participants to report any physical or social harm to the study staff immediately, so that participants may receive counseling or other assistance. When necessary, referrals to a psychiatrist or physician will be made.

**Responsibility for Data and Safety Monitoring.** The PI and mentor are ultimately responsible for data and safety monitoring. The QA processes above ensure that the PI and mentor will be aware of important study-related issues on a weekly basis. The PI will monitor all day-to-day study procedures. If an adverse event occurs, the PI will immediately report the event to the mentor, or in her absence, co-investigator [name], mPI of the parent grant.

We will establish a safety monitoring committee (SMC) comprising at least three people. The SMC will meet at the outset of the study in person then semi-annually by telephone or in person. The semi-annual SMC meeting will assess whether study objectives are being met and will ensure that benefit exceeds harm. The SMC will review the protocol, assessments, and consent forms prior to study initiation. The SMC will receive all reports of AEs at the same time that the AEs are forwarded to the UNC IRB. Severe AEs will trigger an immediate meeting of the SMC. Additional meetings of the SMC can be scheduled, as needed, to discuss and resolve AE issues. Members of the SMC will include at least one representative of local health departments, one substance use treatment professional, and one representative of the substance use research community. The SMC will submit minutes following every meeting to the UNC IRB.

**Staff Training.** All study staff will be trained on confidentiality protection through the university's human subjects training modules prior to beginning their role on the study. The importance of protecting participant confidentiality and any confidentiality issues that arise will be discussed in staff meetings. Should such a violation occur, the study staff must report the event to the PI and mentor immediately after being notified. The study staff will provide the participant with social and emotional support. The study team will try to assist the participant in solving any problems related to loss of confidentiality. A staff member that breaks participant's confidentiality will be put on probation and re-trained on maintaining participant confidentiality. If the same staff member violates a participant's confidentiality a second time, their employment on the study staff will be terminated.

All study staff will be required to complete and maintain valid Human Subjects Research and Good Clinical Practice training certificates from CITI or an equivalent training program prior to working on any aspects of the study.

In addition to reporting of any adverse events, yearly DSM review by the SMC will occur and reports will be sent to the PI, mentor, and co-investigators.

